	 Clinical remission (mPDAI score ≤4 points and a decrease in the baseline mPDAI> 2 points) and no need for antibiotic therapy at week 10 OL. 	
	 Clinical remission (clinical mPDAI score ≤ 4) and no need for antibiotics at week 14 OL. 	
	 Clinical remission (clinical mPDAI score ≤ 4) and no need for antibiotics at week 22 OL. 	
	• Response: Symptomatic improvement of active pouchitis (decrease from baseline in mPDAI clinical subscore ≥ 2 points) and no need for antibiotic therapy at week 10 OL.	
	 Response: Symptomatic improvement of active pouchitis (decrease from baseline in mPDAI clinical subscore ≥ 2 points) and no need for antibiotic therapy at week 14 OL. 	
	 Response: Symptomatic improvement of active pouchitis (decrease from baseline in mPDAI clinical subscore ≥ 2 points) and no need for antibiotic therapy at week 22 OL. 	
	 Symptomatic worsening of active pouchitis (decrease from baseline in mPDAI clinical subscore ≥ 2 points) from FMT week 0 – week 16 Quantitative changes in mPDAI from baseline values 	
	 Quantitative changes of calprotectin from baseline 	
	Alterations in stool microbiome after FMT	
	Engraftment of donor FMT	
Statistical analysis:	Remission and response as defined by mPDAI scores will be analysed by intention-to-treat design. Wilcoxon rank sum tests will be carried out to assess differences in the pre- and post-treatment mPDAI total scores and subscores. P values < 0.05 will be considered to be statistically significant.	
Duration of study	2 weeks of FMT/ placebo therapy followed by evaluation of clinical and endoscopic outcome at week 4, and clinical evaluation at week 8 and 16. In case the study patients does not achieve clinical remission at week 4 or	

	experiences a flare of disease on day 15-28 after start of the study he/she will be offered the possibility to participate in open label extension with an additional endoscopic FMT followed by 2 weeks of oral FMT and clinical follow up at week 10, 14 and 22.
	The anticipated time of the overall study is 18 months
Number of centres:	Single center study

2. BACKGROUND:

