- Engraftment of donor FMT
- Alterations in stool microbiome before and after FMT in study patients with antibiotic dependent pouchitis

Since the bacterial dysbiosis in the pouch plays an important role in the pathogenesis of pouchitis a secondary endpoint is the evaluation of the fecal microfloral pattern by 16S rDNA collected before and 2,4,8 and 16 weeks after FMT.

• Evaluation of calprotectin as a marker of pouch inflammation before and after FMT Repeated pouchoscopies to evaluate the degree of pouch inflammation are not feasible. Also due to safety concerns, biopsies of the pouch will not be taken before FMT. Calprotectin, a member of the S100 family of calcium-binding proteins is abundant in the stool and its level correlates with the endoscopic degree of intestinal inflammation in patients with ulcerative colitis and pouchitis. ^{62, 63} Calprotectin can be readily quantified in feces using enzyme-linked immunosorbent assay (ELISA) or an immunoassay. We will collect stool samples for the measurement of calprotectin at the screening visit and on weeks 2, 4, 8 and 12 after FMT.

6. STUDY DESIGN

• Study Population

The study will include 20 patients who have undergone total proctocolectomy and ileal pouch-anal anastomosis (IPAA) for ulcerative colitis (UC). The study patient qualifies for the study if he/she has episode of active pouchitis, defined as a mPDAI \geq 5 and a history of > 3 antibiotic therapies for pouchitis in the last 12 months or if he/she is in need for chronic antibiotic therapy to maintain clinical remission and has history of at least 2 attempts in the last 24 months to stop continuous antibiotic therapy resulting in pouchitis episodes.

• Treatment period.

2 weeks of FMT/ placebo therapy followed by evaluation of clinical and endoscopic outcome at week 4, and clinical evaluation at week 8 and 16. In case the study patient does not achieve clinical remission at week 4 or experiences a flare of disease on day 15-28 after start of the study he/she will be offered the possibility to participate in open label extension with an additional endoscopic FMT followed by 2 weeks of oral FMT and clinical follow up at week 4, 8 and 16.

- Inclusion Criteria
- Signed informed consent.
- Man or woman between 18 and 70 years of age.
- IPAA after colectomy for ulcerative colitis
- The subject has been diagnosed with one of the following 2 pouchitis subtypes:

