- Response: Symptomatic improvement of active pouchitis (decrease from baseline in mPDAI clinical subscore ≥ 2 points) and no need for antibiotic therapy at week 4.
- Response: Symptomatic improvement of active pouchitis (decrease from baseline in mPDAI clinical subscore ≥ 2 points) and no need for antibiotic therapy at week 8*.
- Response: Symptomatic improvement of active pouchitis (decrease from baseline in mPDAI clinical subscore ≥ 2 points) and no need for antibiotic therapy at week 16*.

*Only patients who do not continue in open label extension

- Exploratory analyses (OL=Open label):
- Endoscopic improvement of active pouchitis (decrease from baseline in mPDAI endoscopic subscore ≥ 2 points) at in open label extension week 8.

- Clinical remission (mPDAI score ≤4 points and a decrease in the baseline mPDAI> 2 points) and no need for antibiotic therapy at week 10 OL.
- Clinical remission (clinical mPDAI score ≤ 4) and no need for antibiotics at week 14 OL.
- Clinical remission (clinical mPDAI score ≤ 4) and no need for antibiotics at week 22 OL.
- Response: Symptomatic improvement of active pouchitis (decrease from baseline in mPDAI clinical subscore ≥ 2 points) and no need for antibiotic therapy at week 10 OL.
- Response: Symptomatic improvement of active pouchitis (decrease from baseline in mPDAI clinical subscore ≥ 2 points) and no need for antibiotic therapy at week 14 OL.
- Response: Symptomatic improvement of active pouchitis (decrease from baseline in mPDAI clinical subscore ≥ 2 points) and no need for antibiotic therapy at week 22 OL.
- Symptomatic worsening of active pouchitis (decrease from baseline in mPDAI clinical subscore ≥ 2 points) from FMT week 0 week 16
- Quantitative changes in mPDAI from baseline values
- Quantitative changes of calprotectin from baseline
- Alterations in stool microbiome after FMT
- Engraftment of donor FMT

Clinical analyses

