The primary endpoint is the evaluation of safety and tolerability of FMT in patients with ADP. Secondary endpoints are endoscopic and clinical remission at week 4 in conjunction with no need for antibiotic therapy, clinical response and remission and no need for antibiotics at week 4,8 and 16, endoscopic improvement of pouchitis and quantitative changes of calprotectin after the initial FMT. All subjects with missing data for determination of endpoint status will be considered as a non-responder in the intention-to-treat analysis. For dichotomous outcomes we will compute the percentage of subjects having the event along with a 95% confidence interval. For continuous outcomes we will compute the mean and a 95% confidence interval for the mean as well as descriptive statistics such as median, range and upper and lower quartiles. In addition to computing these measures for all 20 subjects, we will compute them for subgroups of interest (e.g. endoscopic active vs inactive ADP). These estimates can then be used in the planning of a larger, hypothesis-based study.

• Sample size calculation

This trial is designed as a proof-of-concept study of FMT therapy, not a definitive evaluation of FMT therapy in patients with ADP. The goal is to evaluate the safety and feasibility of such a trial, as well as to estimate the effect sizes in placebo and FMT therapy groups in order to accurately estimate the sample size needed for subsequent evaluation in a larger definitive trial. Nonetheless, we estimated the minimum effect size this pilot study can detect. We assume a placebo remission rate (defined as clinical remission and no need for antibiotics) of 10%. The low placebo response rate is based on the inclusion criterion, which selects only patients needing continuous or recurrent antibiotic therapy in the setting of ADP. With a follow-up of 16 weeks with the requirement of clinical remission without antibiotic therapy at end of follow-up, a placebo response rate beyond 10% is highly unlikely. The recent case series of Stallmach et al. suggests an antibiotic-free remission rate of 80% and a response rate of 100% in the setting of repeated FMT.⁴⁹ With 20 patients (1:1 randomization), and a placebo response rate of 10%, we will have 80% power to detect an effect difference of 67.5%, that is, an antibiotic-free remission rate

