of 77.5% in the treatment group (2-sided, alpha=0.05, Fisher-Irwin's exact conditional test). Thus, even with this small proof-of-concept design, we could observe a significant effect in the range of effect size reported in recent case series.

Microbiome Analyses

From each patient 1 stool sample will be collected before transplant and twice after the transplant (week 3 and 4). Patients in remission will collect 2 more stool samples in week 8 and 16. Patients in the open label extension trial will collect stool samples after transplant in week 8, 10, 14 and 22. Assuming that 9 patients enter remission in the placebo controlled phase (9x4= 36 samples) and 11 patients enter the open label extension (11x7=77 samples) a total of 116 samples will be analysed. All microbiome analyses will be conducted by OpenBiome, which will donate time and materials for the analyses. The gut microbiome of donors and patients will be analysed through deep sequencing of the 16S ribosomal RNA gene amplified from stool samples. Microbial engraftment will be operationalized through the donor similarity index (DSI) used to evaluate the degree of engraftment in FMT recipients over time (after 2,4,8 and16 weeks).⁶¹ We will measure DSI over time to elucidate the stability of engraftment and its relationship to clinical observations. In addition to 16S rRNA sequencing, we will save aliquots of stool for metabolomic characterization. In particular, given the potential role of butyrate in ameliorating inflammation, we're especially interested in measuring short chain fatty acid levels in stool before and after FMT. We plan to collect stool samples for characterization at baseline and at 2, 4, 8 and 16 week intervals after treatment.

21. STUDY VISITS CHART

1.1 STUDY VISITS CHART PLACEBO CONTROLLED TRIAL SCREENING – WEEK 4 (SITE VISIT)

Visit	Screening	1	2	3	4	5	Early termination ^g
Type of visit	Site	Site	Phone	Site	Phone	Site	Phone/site
Derr	-14	0	7	15	26	28	
Day	-14	0	+/-1	+3	+/-1	+/-3	
Week	-2	0	1	2	4	4	
Medical History	Х						
mPDAI score		Х	Xd	X ^d	X ^{g(!)}	Х	X
Concomitant Medication	Х	Х	X	X	X	Х	X
Adverse Events		Х	X	Х	Х	Х	X
Physical Exam	Х					Х	Х
Blood Tests	Х					Х	Х
Pregnancy Test (urine)	Х	Х					
Test FMT capsule	Х						
Dispense FMT capsules		Х					
10-14 day antibiotic therapy pre- transplant	Х				Xc	Xc	Xc
Stool sample	Xe			X ^f	X ^f	X ^g	Х
Sigmoidoscopy (Pouchoscopy		Х				Xa	
Endoscopic FMT		Х					
Distribute/Review Subject Diaries ^b	Х	Х	Х	Х	Х	Х	Х

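### The week-8 and week-16 remission and response endpoints leave out patients who enter the open-label extension, so their denominators are selected on a post-randomisation outcome, contrary to the plan's own intention-to-treat rules

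*Combined protocol and SAP*

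**What the plan says.** Four secondary endpoints carry an asterisk: clinical remission at weeks 8 and 16, and response at weeks 8 and 16. The asterisk reads "Only patients who do not continue in open label extension". It appears in the Protocol Summary (Section 1), in Trial Endpoints (Section 5) and in Statistical Analysis (Section 20).

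Section 6 (Treatment period) gives the condition for the extension: "In case the study patient does not achieve clinical remission at week 4 or experiences a flare of disease on day 15-28 after start". Such a patient is offered a second endoscopic FMT followed by oral FMT. Section 7 lets patients decline, and decliners follow the same visit schedule as patients in remission. Section 7 also requires at least 10 days of antibiotics before the open-label FMT.

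Three other statements govern the same endpoints:

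- Section 1, Statistical analysis: "Remission and response as defined by mPDAI scores will be analysed by intention-to-treat design".
- Section 20, Clinical analyses: "All subjects with missing data for determination of endpoint status will be considered as a non-responder in the intention-to-treat analysis".
- Section 20, Clinical analyses: "In addition to computing these measures for all 20 subjects, we will compute them for subgroups of interest".

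The Clinical analyses text lists remission and response at weeks 4, 8 and 16 without repeating the restriction. No section says how an extension entrant is scored at week 8 or week 16.

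**The concern.** The footnote and the intention-to-treat rules cannot both govern the same four endpoints. Under the footnote, the denominator holds week-4 remitters plus those non-remitters who declined the extension. Membership depends on the week-4 result, which is close to the endpoint itself, and on patient choice. The groups compared are then no longer the randomised groups, and most of those removed have already failed on remission.

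This matters because Section 20 (Sample size calculation) names this goal: "estimate the effect sizes in placebo and FMT therapy groups in order to accurately estimate the sample size needed for subsequent evaluation". The evaluation meant is the next, definitive trial. A rate among patients who did not enter the extension answers a different question, namely how durable the result is in a selected subset. If it is carried forward as an arm-level rate, it will be too high.

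Because no scoring rule is given, an analyst could also choose after seeing the data whether to exclude entrants, score them as failures, or use a score taken after the second FMT. Under the last option, a placebo patient given open-label FMT could count as a placebo remission.

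**Working it through.** **Inputs.** 20 patients, 1:1, so 10 per arm; placebo rate 10% and FMT rate 77.5% (Section 20, Sample size calculation). Pooled split: "Assuming that 9 patients enter remission in the placebo controlled phase (9x4= 36 samples) and 11 patients enter the open label extension" (Section 20, Microbiome Analyses).

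**Plan's own figures.** An exact two-sided Fisher test at 0.05 with 10 v 10 and 10% v 77.5% has power 80.2%, which agrees with the stated 80%. Expected remitters are 10 × 0.775 + 10 × 0.10 = 7.75 + 1.0 = 8.75, consistent with the plan's 9.

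**Pooled rate at week 8 or 16, plan's split, all 11 entering (exact 95% CI).**

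| Remitters who stay in remission (assumption) | Footnote denominator | All randomised |
|---|---|---|
| 9 of 9 | 9/9 = 100% (66.4–100) | 9/20 = 45% (23.1–68.5) |
| 6 of 9 | 6/9 = 67% (29.9–92.5) | 6/20 = 30% (11.9–54.3) |

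If k of the 11 decline and remain as non-remitters, the first row's footnote rate becomes 9/(9 + k): 75% at k = 3, 60% at k = 6, and 45% at k = 11 (no distortion).

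**By arm, full entry.** The plan does not split the 9 by arm. Assume 8 FMT and 1 placebo, all sustained. The footnote gives 8/8 v 1/1, a difference of 0. All randomised gives 8/10 v 1/10, a difference of 70 points.

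**By arm, partial entry.** Let u be the share of non-remitters who enter (assumption, equal in both arms), with week-4 remission sustained. The rate under the footnote is p / [p + (1 − p)(1 − u)].

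At u = 50%: placebo 0.10/(0.10 + 0.90 × 0.5) = 18.2%; FMT 0.775/(0.775 + 0.225 × 0.5) = 87.3%.

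| u | Placebo | FMT | Difference (points) |
|---|---|---|---|
| 0% | 10.0% | 77.5% | 67.5 |
| 25% | 12.9% | 82.1% | 69.2 |
| 50% | 18.2% | 87.3% | 69.1 |
| 75% | 30.8% | 93.2% | 62.5 |
| 90% | 52.6% | 97.2% | 44.5 |
| 100% | 100% | 100% | 0 |

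**Does the missing-data rule put entrants back?** The Section 21 chart places the second FMT at day 38.

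- Week-8 window (Section 9, Visit 7): 56 ± 5 = days 51–61. Visit 8OL: 38 + 15 = day 53, +3, so days 53–56. This is inside the window, so a clinical mPDAI exists, but it follows the second FMT.
- Week-16 window (Section 9, Visit 8): 112 ± 7 = days 105–119. Visit 11OL: 94 ± 5 = days 89–99. Visit 12OL: day 150, giving 145–155 with the ± 5 of Section 10 or 143–157 with the ± 7 of the chart. Neither visit falls inside the window. The stool diary runs to 12OL (Section 7), so symptom data may still exist.

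These days move with the date of the second FMT. A flare on day 7 (Section 7 allows days 1–28) plus 10 days gives a second FMT at day 17 and 8OL at days 32–35, outside the week-8 window. Visit 5 on day 31 plus 14 days gives day 45: 8OL is then days 60–63, and 11OL is 101 ± 5 = days 96–106, which touches the week-16 window. Whether an entrant has missing status therefore depends on timing.

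**The case against.** The best defence is that the footnote only routes patients between schedules. Visits 7 and 8 exist only for patients who do not enter the extension, and entrants have their own exploratory endpoints at weeks 10, 14 and 22. The Clinical analyses text then names weeks 4, 8 and 16 without restriction, counts missing as non-response and uses all 20 subjects. On that reading entrants are simply failures. This is a possible intention, and a reader should not infer that the sponsor means to discard failures. But no section states it, the footnote is attached to the endpoints inside the statistical section itself, and the missing-data rule does not reliably reach entrants, some of whom will have a week-8 score.

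Two further points stand. First, a reader might infer from 8/8 v 1/1 that the treatment difference disappears. That needs nearly every non-remitter to enter; the plan assumes full entry only to count stool samples, and up to 75% entry the difference stays between 62 and 70 points. Second, a reader might infer that entrants always have a week-8 score and never a week-16 visit. That holds only on the nominal day-38 schedule.

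It is also fair that scoring every entrant as a failure is one strategy among several. The Section 21 chart title admits patients with response only, so some entrants may be week-4 responders.

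**Conclusion.** Wrong as written. The footnote defines the week-8 and week-16 remission and response denominators by a post-randomisation outcome and contradicts the plan's intention-to-treat, all-20 and missing-as-non-response rules. On the plan's 9/11 split with sustained remission, the pooled rate moves from 45% to 100%. At 50% entry, the arm rates move from 10% and 77.5% to about 18% and 87%.

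These sizes assume that week-4 remitters stay in remission (except the 6-of-9 row) and that decliners remain non-remitters. Extension uptake and the arm split are not in the documents. Only remission is quantified. For response the selection is the same, but its size and direction are less clear because some entrants may be responders.

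A reader might go further and infer that the trial's main results or its power figure are compromised. The documents do not support that. Week-4 remission and response and the primary safety endpoint carry no footnote, and the 80% power reproduces for 10 v 10. The affected endpoints are secondary, in a proof-of-concept trial. The point should be fixed because those rates are meant to inform the next trial.

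**What to change.** In Sections 1, 5 and 20, replace the footnote with a rule that week-8 and week-16 remission and response are analysed in all randomised patients by arm, and that entry to the open-label extension or need for antibiotics for pouchitis counts as not meeting the endpoint at those time points. This fits the endpoint's antibiotic-free component, since open-label FMT is preceded by at least 10 days of antibiotics. It also removes any dependence on when visits 8OL, 11OL and 12OL happen to fall.

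Keep the non-extension subset as a descriptive durability summary, labelled as non-randomised. If the footnote was meant only to describe visit attendance, say so and still state how entrants are scored.

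The cost is wording only: extension entry and concomitant medication are already recorded. The downsides are lower reported week-8 and week-16 rates, and that patients with response only who choose the extension count as failures at those time points. If the sponsor prefers another handling of entrants, it should be fixed in the plan before unblinding.

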	The outcome will be determined by the modified pouchitis disease activity index (mPDAI) and the need for antibiotic therapy to control symptoms. The mPDAI is a composite index consisting of 2 disease variables (clinical criteria of pouchitis: number of bowel movements, blood in stool, urgency and fever with a maximum score of 6 and endoscopy criteria of pouch inflammation with a maximum score of 6. The maximum combined score is 12).	
	 Complete remission is defined as a mPDAI score = 0 and no need for antibiotics. Clinical remission is defined as a clinical mPDAI score ≤ 4 and no need for antibiotics. Symptomatic improvement is defined as a decrease from baseline in the mPDAI clinical subscore of 2 points and no need for antibiotics. Symptomatic worsening of the disease is defined by an increase in the mPDAI clinical subscore of 2 points or the need for antibiotics. 	
	The severity of the pouch inflammation will be evaluated by two pouchoscopies (week 0 and week 4). Endoscopic improvement is defined as a decrease from baseline in the mPDAI endoscopic subscore of 2 points.	
Primary variables	Safety and tolerability of endoscopically and orally applied FMT	
Secondary variables:	 Clinical remission (mPDAI score ≤4 points) and no need for antibiotic therapy at week 4. Clinical remission (clinical mPDAI score ≤ 4) and no need for antibiotics at week 8*. Clinical remission (clinical mPDAI score ≤ 4) and no need for antibiotics at week 16*. Endoscopic improvement of active pouchitis (decrease from baseline in mPDAI endoscopic subscore ≥ 2 points) at week 4. 	

	 Response: Symptomatic improvement of active pouchitis (decrease from baseline in mPDAI clinical subscore ≥ 2 points) and no need for antibiotic therapy at week 4. Response: Symptomatic improvement of active pouchitis (decrease from baseline in mPDAI clinical subscore ≥ 2 points) and no need for antibiotic therapy at week 8*. Response: Symptomatic improvement of active pouchitis (decrease from baseline in mPDAI clinical subscore ≥ 2 points) and no need for antibiotic therapy at week 8*. Response: Symptomatic improvement of active pouchitis (decrease from baseline in mPDAI clinical subscore ≥ 2 points) and no need for antibiotic therapy at week 16*. 	
	*Only patients who do not continue in open label extension	
	• Exploratory analyses (OL=Open label):	
	 Endoscopic improvement of active pouchitis (decrease from baseline in mPDAI endoscopic subscore ≥ 2 points) at in open label extension week 8. 	

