The 9OL site visit will review adverse events and the adverse event diary, collect safety blood labs, perform a physical exam and calculate the mPDAI. A stool sample for the stool bank will be collected from the patient. A pouchoscopy will also be performed.

Phone visit 10OL will evaluate for adverse events and review the adverse event diary. At this point 4 weeks after stopping the oral FMT the patient can stop filling out the daily adverse event diary The patient will be reminded to bring the filled out adverse event diary to site visit 11OL. Additionally, mPDAI will be calculated and the concomitant medications will be assessed.

Site visit 110Lwill collect all pages of the adverse event diary, and review the adverse events, which occurred since visit 100L. A physical exam and blood tests will be performed and the mPDAI will be calculated. The concomitant medications will be reviewed. A stool sample for the stool bank will be collected from the patient.

Site visit 12OL will review new adverse events, concomitant medications and the mPDAI score. A stool sample for the stool bank will be collected from the patient.

On the last phone visit 13OL the coordinator will review serious adverse events only, which may have occurred since visit 12OL.

Study patients experiencing a recurrence of symptoms in the open label extension period

If the study patient is experiencing worsening of disease after the second FMT, antibiotic therapy will be re-initiated as a standard of care approach. The patient will nevertheless be followed up according to the same schedule as patients not experiencing a relapse.

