The rectal bleeding frequency will be calculated for the three evaluation days. The relative frequency for rectal bleeding will be calculated based on the total number of stools passed over the same three evaluation days ((total #stools with blood/total #stools)*100). The relative frequency will be evaluated against the following categories:

0% (none) < 20% (rare) > 20% (present daily)

Please note that the words, "none", "rare", and "present daily" in parentheses, correspond to the rectal bleeding categories on the mPDAI. These categories will be used to assign a mPDAI score for rectal bleeding.

Fecal urgency/abdominal cramping

The fecal urgency/abdominal cramping frequency will be calculated for the three evaluation days. The relative frequency for fecal urgency/abdominal cramping will be calculated based on the total number of stools for the same three evaluation days ((total #stools with cramping or urgency/total #stools)*100). The relative frequency will be evaluated against the following categories:

0% (none) < 50% (occasional) > 50% (frequent)

As with rectal bleeding, the words, "none", "occasional", and "frequent" in parentheses, correspond to the fecal urgency/abdominal cramping categories on the mPDAI. These categories will be used to assign a mPDAI score for fecal urgency/abdominal cramping.

Fever

If a subject indicates that they had a fever on none of the three evaluation days, the mPDAI score for "absent" will be recorded. If a subject indicates that they had a fever on one or more of the three evaluation days, the mPDAI score for "present" will be recorded.

20. STATISTICAL ANALYSIS

The following endpoints will be assessed

• Primary Endpoint:

Safety and Tolerability of FMT

- Number of study patients, who discontinued therapy
- Adverse events grouped by body system
- Changes in laboratory values
- Secondary Endpoints Clinical remission (mPDAI score <4 points and a decrease in the baseline mPDAI > 2 points) and no need for antibiotic therapy at week 4.
- Clinical remission (clinical mPDAI score ≤ 4) and no need for antibiotics at week 8*.
- Clinical remission (clinical mPDAI score ≤ 4) and no need for antibiotics at week 16*.
- Endoscopic improvement of active pouchitis (decrease from baseline in mPDAI endoscopic subscore ≥ 2 points) at week 4.

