Distribute/Review Subject adverse events diary ^b			Х	X	X	X	Х

Study visits Chart for patients continuing in observation phase

Visit	6	7	8	9	Early termination ^g
Type of visit	Phone	Site	Site	Phone	Phone/site
Day	42	56	112	168	
	+/-3	+/-5	+/-7	+/-10	
Week	6	8	16	24	
mPDAI score	Х	X ^d	X ^d		Х
Concomitant Medication	Х	Х	X		Х
Adverse Events	Х	Х	X	X ^I	Х
Physical Exam		Х			Х
Blood Tests ^a		Х			Х
Stool sample		Xf	Xf		
Sigmoidoscopy (Pouchoscopy					
Distribute/Review Subject Diaries ^b	Х	Х			Х
Distribute/Review Subject adverse events diary ^b	Х	Xj			X

1.2 STUDY VISITS CHART OPEN LABEL EXTENSION FOR PATIENTS WITH RESPONSE ONLY OR NO RESPONSE OR EARLY TERMINATION DUE TO FLARE IN PLACEBO-CONTROLLED TRIAL SECTION

Visit	60L	70L	80L	90L	100L	110L	120L	130L	Early termination ^g
Type of visit	Site	Phone	Site	Site	Phone	Site	Site	Phone	Phone/site
Day (post 2nd transplant)	38 (0)	46 (8)	53 (15)	66 (28)	80 (42)	94 (56)	150 (112)	206 (168)	
38 (0)	38 (0)	+/-1	+3	+/-3	+/-3	+/-5	+/-7	+/-10	
Week (post 2nd transplant)	6 (0)	7 (1)	8 (2)	10 (4)	12 (6)	14 (8)	22 (16)	30 (24)	
mPDAI score		X ^d	X ^d	Х	Х	X ^d	X ^d		Х
Concomitant Medication	Х	Х	Х	Х	Х	Х	Х		Х
Adverse Events	Х	Х	Х	Х	Х	Х	Х	XI	Х
Physical Exam	Х			Х		Х			Х
Blood Tests				Х		Х			Х
Pregnacy test (urine)	Х								
Dispense FMT capsules + omeprazole	X ^g								
Stool sample			Xf	Xf		Xf	Xf		Х
Sigmoidoscopy (Pouchoscopy	Х			Х					
Endoscopic FMT	X ^h								
Distribute/Review Subject PDAI Diary ^b	Х	Х	Х	Х	Х	Х	Х		X
Distribute/Review Subject adverse events diary ^b	Х	Х	Х	Х	Х	Xj			X

^a Pouchoscopy visit 5 only in patients who are in remission (mPDAI<4) as assessed in visit 4 by phone or in patients with clinical active pouchitis, but not willing to participate in open label extension

^b There will be two subject diaries provided to the patient: One for the evaluation of the mPDAI will be provided at Screening. The study patient will complete this diary each day, beginning with the Screening visit, and ending with the Week 16 visit. Stool frequency, rectal bleeding, fecal urgency or abdominal cramps, and/or fever will be recorded. A minimum of three days of diary entries will be required during the week prior to randomization, Phone visit week 1 and 2 and Visit Week 4 and 8. The last three days of diary entries will be used to calculate stool frequency and fecal urgency/abdominal pain scores and clinical mPDAI subscores.

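### Endoscopic improvement is the only efficacy success endpoint with no antibiotic-free condition, so a relapsed patient back on antibiotics can count as improved at visit 9OL

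*Combined protocol and SAP*

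**What the plan says.** **Definition.** Section 1 (Criteria for Evaluation) bases the outcome on the mPDAI together with whether antibiotics are needed to control symptoms. It attaches the antibiotic condition to complete remission, clinical remission and symptomatic improvement. For the mucosal measure it says only: "Endoscopic improvement is defined as a decrease from baseline in the mPDAI endoscopic subscore of 2 points".

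**Endpoint lists (Sections 1, 5 and 20).** The week 4 secondary endpoint is "Endoscopic improvement of active pouchitis (decrease from baseline in mPDAI endoscopic subscore ≥ 2 points) at week 4". The extension endpoint has the same form: "Endoscopic improvement of active pouchitis (decrease from baseline in mPDAI endoscopic subscore ≥ 2 points) at in open label extension week 8". The neighbouring extension endpoints do carry the condition: "Clinical remission (clinical mPDAI score ≤ 4) and no need for antibiotics at week 14 OL", and the week 10 remission and response items end "and no need for antibiotic therapy at week 10 OL".

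**Extension conduct (Section 7).** If disease worsens after the second FMT, antibiotics are restarted. "The patient will nevertheless be followed up according to the same schedule as patients not experiencing a relapse". Of visit 9OL the section says: "A pouchoscopy will also be performed". Section 10 and the extension chart in Section 21 also place a pouchoscopy at 9OL, with no condition on remission or antibiotics.

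**Week 4 conduct.** Section 8 (Visit 5) restricts the pouchoscopy to patients in clinical remission who do not need antibiotics. Footnote a to the Section 21 charts also allows it "in patients with clinical active pouchitis, but not willing to participate in open label extension".

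**Handling rule.** Section 20 (Clinical analyses) counts patients with missing endpoint data as non-responders. It says nothing about an observed score obtained on antibiotics.

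**The concern.** The trial asks whether FMT can replace antibiotics in antibiotic-dependent patients, so success is elsewhere defined as success without them. Endoscopic improvement departs from that without saying so. In the extension there is no control group, and 9OL is the only pouchoscopy after the second FMT. A patient in whom FMT failed, who was put back on antibiotics and then scoped, can therefore enter the only open-label mucosal rate as improved after FMT. Section 20 says its estimates are to be used in planning a larger study. A reader of the rate could not tell how much of it was obtained on antibiotics.

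**Working it through.** **1. Is the condition missing only here?** Going through the endpoint lists in Sections 1, 5 and 20:

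| Endpoint | Antibiotic-free condition |
|---|---|
| Clinical remission, weeks 4, 8, 16 and OL 10, 14, 22 | yes |
| Response, weeks 4, 8, 16 and OL 10, 14, 22 | yes |
| Endoscopic improvement, week 4 | no |
| Endoscopic improvement, extension | no |

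Symptomatic worsening is also listed without it, but it is not a success endpoint, and its Section 1 definition counts need for antibiotics as worsening. Section 20 (Clinical analyses) ties endoscopic and clinical remission at week 4 to being off antibiotics, then names endoscopic improvement without that tie.

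**2. Can a patient on antibiotics reach the endpoint in the extension?** Relapse leads to antibiotics; the schedule is unchanged; 9OL takes place 28 ± 3 days after the second transplant; the pouchoscopy is unconditional. The score is observed, so the missing-data rule does not apply. Sections 1 and 6 list antibiotics for pouchitis as not permitted but attach no analysis consequence. Illustration with assumed scores: baseline endoscopic subscore 4, relapse, antibiotics restarted, subscore 2 at 9OL. The fall is 4 − 2 = 2, so the patient fails remission and response and counts as endoscopically improved.

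**3. Which visit feeds the endpoint?** It is labelled week 8. Study week 8 is visit 8OL and OL week 8 is visit 11OL; neither has a pouchoscopy. The only one after the second FMT is 9OL (study week 10, OL week 4). Read literally, every score would be missing and every patient a non-responder. The heading in Section 11 also omits 9OL from its list of pouchoscopies. The steps here take 9OL as the visit.

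**4. Size.** Section 20 (Microbiome Analyses) assumes 11 extension patients. One reclassified patient shifts the rate by 1/11 = 9.1 percentage points. To show the effect on what would be reported, assume 3 improvers off antibiotics; the documents do not give this figure. The intervals are exact (Clopper-Pearson), since the plan promises 95% intervals without naming a method.

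| Improvers on antibiotics | Rate as written | 95% CI |
|---|---|---|
| 0 (also the rate if the condition is added) | 3/11 = 27.3% | 6.0 to 61.0 |
| 1 | 4/11 = 36.4% | 10.9 to 69.2 |
| 2 | 5/11 = 45.5% | 16.7 to 76.6 |
| 3 | 6/11 = 54.5% | 23.4 to 83.3 |

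**5. The plan's own figure.** Section 20 states 80% power for antibiotic-free remission of 77.5% against 10%, with 20 patients randomized 1:1, two-sided alpha 0.05 and Fisher's exact test. Summing the binomial probabilities of all 11 × 11 outcomes with p ≤ 0.05 gives 0.8016, so the figure reproduces. It does not involve the endoscopic endpoint.

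**6. Week 4.** Under Section 8 no patient needing antibiotics is scoped at visit 5. Under footnote a, patients with active disease who decline the extension are scoped. Section 7 allows antibiotics from phone visit 4, with visit 5 in the next 3 to 4 days (Section 8 puts the call 2 to 3 days before visit 5). Any such patient has therefore had roughly 2 to 4 days of antibiotics.

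**The case against.** The strongest counter-argument concerns baseline. All patients take antibiotics for at least 10 days before week 0, stopping 24 hours before FMT (Section 7). Visit 6OL, the other possible baseline, also follows at least 10 days of antibiotics. A relapser put back on antibiotics would more naturally return towards that level than fall 2 points below it, and a patient with a baseline subscore of 0 or 1 cannot qualify at all. This stands as a reason to expect few such patients. It does not exclude them: a relapse before about day 18 leaves more than 28 − 18 = 10 days of renewed antibiotics by day 28, and the plan does not say which baseline applies.

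Second, a mucosal measure scored regardless of rescue is a legitimate choice, and antibiotic-free remission and response are reported at the same visit. That one patient can fail clinically and improve endoscopically is not an error in itself. However, the plan does not state that choice, and it departs from the outcome principle in Section 1. Some on-antibiotic improvers might also have improved after FMT alone, so 9.1 points is the difference between two scoring rules, not a measured bias.

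Third, a reader might infer a large upward bias by multiplying a relapse share by a share who heal on antibiotics. The documents give neither share. Section 2 cites the clinical efficacy of antibiotics, not mucosal healing, so no such range is supported. A reader might also infer that week 4 is equally exposed. Section 8 argues against that; only footnote a opens the gap.

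**Conclusion.** The point holds, as an analysis rule worth correcting rather than a threat to the trial. Followed as written, the rule can credit FMT with an endoscopic improvement in a patient whom FMT failed and who was scoped on antibiotics. The size is 9.1 points per such patient at n = 11. The number of such patients is unknown and probably small, given the antibiotic-treated baseline. This rests on 9OL being the visit that feeds the endpoint, which is the only workable reading, and on the assumed 11 entrants.

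At week 4 the gap is narrow and depends on which of two conflicting provisions is followed. The extension endpoint is exploratory and uncontrolled. The stated 80% power and the primary safety endpoint do not change, and nothing in the documents supports inferring that they do.

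**What to change.** In Sections 1, 5 and 20:

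- Add to endoscopic improvement, at week 4 and in the extension, the same antibiotic condition that remission and response carry, applied at the assessment visit. A longer look-back would be a different rule from the one those endpoints state.
- Count a patient on antibiotics for pouchitis at the pouchoscopy as not improved.
- List observed endoscopic subscores separately by antibiotic status, so that no data are lost.
- Name 9OL as the extension visit in place of week 8, and state whether baseline is week 0 or 6OL.
- Reconcile the Visit 5 pouchoscopy restriction in Section 8 with footnote a in Section 21.

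The cost is a clause, a listing and two clarifications. Concomitant medication is already reviewed at visits 5 and 9OL, so antibiotic status at the visit should be available. The downside is that the reported improvement rate may be lower. Patient management, sample size and the primary endpoint stay as they are.
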